3.3.2 Safety Population

The Safety population will consist of all patients who receive at least one dose of any study medication.

3.4 Calculated Variables

- Study day 1 is defined as the first day any of the study therapy was received.
- The baseline is defined as the last assessment done before or on study day 1.
- Duration of Response (months): (earliest date of censoring, progression, or death – earliest date of response + 1) * 365.25 / 12.
- The cycle start date is the first date of administration of any study drug (with a non-missing dose) by treatment cycle (as reported in the eCRF).
- The visit of premature discontinuation of each drug will be derived from [the date of the last dose reported on the form of discontinuation. This date will be merged with the date of drug administration to determine to which cycle of treatment it corresponds.

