2.9 Translational opportunities

Pre-clinical and clinical data suggest that combination of immune checkpoint inhibitors targeting non-overlapping pathways such as durvalumab and tremelimumab may induce synergistic effect leading to improved tumor response in comparison to monotherapy with either agent alone. We hypothesize that the combination of radiation and dual immune checkpoint blockade with durvalumab plus tremelimumab may have synergistic effect on effector T cell activation ([Pardoll 2012](#)).

This study serves as a platform allowing for detailed assessment of the mechanisms of immune stimulation, predictive markers of response or resistance and rational development of the next generation of combination immunomodulatory interventions ([Taube 2014](#), [Topalian 2012](#)). Samples will be collected that may be used in post-hoc analyses including but, not limited to:

- peripheral lymphocytes analysis for immune cell gene expression and quantitative changes of lymphocyte subpopulation and immune-related cells.
- collection of tumor tissues from unirradiated tumor sites prior to radiation and after two cycles of therapy for further analysis of immune response in tumor.
- analysis of gene expression related to immune checkpoint pathways.
- analysis of frequency of mutation-associated neoantigens in tumor tissues.

3.0 **STUDY AIMS AND ENDPOINTS**

3.1 **Primary aim and endpoint**

Aim: To determine the efficacy of the dual immune checkpoint blockade with durvalumab plus tremelimumab following a small dose of hypofractionated palliative radiation in patients with MSS mCRC who have progressed on chemotherapy.

Endpoint: Overall objective response rate (ORR) as measured by RECIST 1.1 criteria.

3.2 **Secondary aims and endpoints**

3.2.1 ***Clinical benefit rate***

Aim: To determine objective tumor decrease and stable disease (SD) at 16 weeks.

Endpoint: Measurement of disease status by continuous tumor measurement (any partial response [PR], any complete response [CR] and SD at 16 weeks).

3.2.2 ***Duration of response***

Aim: To determine the duration of response of mCRC to study therapy.

Endpoint: Measurement of time from study entry until documentation of progression as determined by RECIST 1.1.

3.2.3 ***Safety and Toxicity***

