11.0 ASSESSMENT OF EFFECT

Response to study treatment in this patient population will follow standard RECIST criteria except in the documentation of progressive disease (PD). In this protocol, patients with progressive radiographic metastatic disease who are clinically asymptomatic and without other significant reason to discontinue therapy (i.e., toxicity, physician's judgement or patient's decision to stop therapy) may continue to receive study therapy per protocol until the next scheduled tumor assessment ([Table 2](#)) to confirm progression. If progression is confirmed the date of progression will be at the time of the initial scan indicating progression.

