12.2 Study entry

DSSM will verify that the research site has current IRB approval for the study. Entry will not take place if the IRB approval is not current with IRB oversight responsibility.

All patients must be enrolled through DSSM. Once the entry eCRFs have begun to be entered, submit copies of the redacted signed consent form, and supporting documents to

The entry material must be received by DSSM **no later than 4:00 p.m. Eastern Time, Monday through Friday, excluding holidays**. Once received the review process will begin. When the review is complete and approved, an enrollment confirmation will be sent. **This process could involve some unavoidable delays. Therefore, it is necessary to plan adequate time (at least 24 hours) between study entry and the initiation of the patient's study therapy.**

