7.2.1 Clinical Benefit Rate

CBR is defined as the proportion of patients with no progression or death at 16 weeks.

The 95% confidence interval of the CBR will be reported using exact method based on the binomial distribution (Clopper-Pearson method). The denominator will be the number of patients in the ITT population.

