7.2.2 Duration of Response

DOR is defined as the time (in months) from best response to progression, censoring, or death) among patients with a response.

The median and a 95 % confidence interval of DOR will be reported using Kaplan-Meier methods.

8. Exploratory Translational Studies

Immune markers will be explored by NSABP out of the scope of this SAP.

9. Appendices

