Appendix 1: List of Statistical Tables

Appendix 2: List of Data Listings

Appendix 1: List of Statistical Tables

Table Number	Table Title	Population
Table 01.01	Patient Disposition	All enrolled patients
Table 01.02	Completion Status and Discontinuation from study drugs	ITT
Table 01.03	Completion Status and Discontinuation from the Study	ITT
Table 02.01	Demographic and Other Baseline Characteristics	ITT
Table 03.01	Extent of Exposure	ITT
Table 04.01	Summary of Adverse Events	Safety
Table 04.02	Grade 1/2 Adverse Events by SOC and PT	Safety
Table 04.03	Grade 3/4 Treatment-Emergent Adverse Events by SOC, PT	Safety
Table 04.04	Adverse Events Leading to Discontinuation of Study Therapies, by SOC and PT	Safety
Table 04.05	Fatal Adverse Events by SOC and PT	Safety
Table 04.06	AEs leading to Death by SOC and PT	Safety
Table 04.07	Deaths	Safety
Table 05.01	Best overall response	ITT
Table 05.02	Objective Response Rate	ITT
Table 05.03	Clinical Benefit Rate at 16 weeks	ITT
Table 05.04	Duration of Response	ITT
Figure 05.05	Kaplan-Meier Duration of Response Plot	ITT

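### SAP 3.4 converts duration of response to months by multiplying where it should divide, and the SAP and protocol give the endpoint three different start dates

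*Combined protocol and SAP*

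**What the plan says.** **Duration of response.** SAP 3.4 gives the calculation, labelled in months, as "earliest date of censoring, progression, or death – earliest date of response + 1) * 365.25 / 12". SAP 7.2.2 states that "DOR is defined as the time (in months) from best response to progression, censoring, or death", among responders, and summarises it by a Kaplan-Meier median with a 95% confidence interval. Protocol 3.2.2 gives the endpoint as "Measurement of time from study entry until documentation of progression as determined by RECIST 1.1". It names neither death nor censoring.

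The calculated values feed Table 05.04, Figure 05.05 ("Kaplan-Meier Duration of Response Plot") and Listing 05.02.

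Two protocol sections bear on the dates. Section 12.2 tells sites to "plan adequate time (at least 24 hours) between study entry and the initiation of the" patient's therapy, so entry comes before Day 1. Section 11.0 says: "If progression is confirmed the date of progression will be at the time of the initial scan indicating progression".

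**Clinical benefit rate (CBR).** SAP 7.2.1 says that "CBR is defined as the proportion of patients with no progression or death at 16 weeks". Protocol 3.2.1 counts "any partial response [PR], any complete response [CR] and SD at 16 weeks".

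**Status.** SAP 7.2 treats the secondary endpoints as descriptive. SAP 3.5 declares no departure from the protocol, and SAP 1 names the protocol version of November 7, 2016.

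**The concern.** There are two separate faults in DOR. The first is a unit error in the one place where the SAP gives a formula to program from. Followed literally, it puts a table, a figure and a listing on the wrong scale.

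The second matters more because nothing in the output would reveal it. With the units corrected, each of the three start dates gives a believable number, so a reader could not tell which had been used. While the start date and the censoring date stay open, they can be settled after the responses are known. Few patients will respond, so one patient's start date can move the median.

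The lesser concern is CBR. The analysis set in SAP 3.3.1 requires only the scan after Cycle 2. A patient in that set can therefore reach week 16 with no scan and no recorded event, and SAP 7.2.1 read literally would count that patient as a benefit.

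**Working it through.** The documents report no DOR value, so there is no figure to reproduce. The check is of units and of start dates.

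**1. Units (SAP 3.4).**
- Days per month: 365.25 / 12 = 30.4375.
- Correct conversion: months = days / 30.4375 = days × 12 / 365.25.
- As printed: days × 30.4375.
- Ratio of printed to correct: 30.4375² = 926.4, the same for every patient.

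| Days | Correct months | As printed |
|---|---|---|
| 1 | 0.03 | 30.4 |
| 169 | 5.55 | 5,143.9 |
| 365 | 11.99 | 11,109.7 |

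The full 24 cycles last 24 × 28 = 672 days, or 22.1 months. Even a one-day DOR would print as longer than that. Because the factor is constant, the shape of the Kaplan-Meier curve is unchanged; only its time axis is wrong.

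**2. Start dates.** Take a hypothetical responder with PR at week 8, CR at week 24 and progression at week 40. Entry is set at week 0, and the SAP's extra day is used for the SAP definitions.
- Protocol 3.2.2, from entry: 280 days / 30.4375 = 9.2 months.
- SAP 3.4, from earliest response: (224 + 1) / 30.4375 = 7.4 months.
- SAP 7.2.2, from best response: (112 + 1) / 30.4375 = 3.7 months.

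Without the CR, both SAP definitions give 7.4. The two SAP start dates therefore differ only when a response deepens.

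The entry start differs for every responder, because it adds the time to response. For a response 56 days after Day 1:
- entry on Day 1: 56 / 30.4375 = 1.84 months;
- entry 24 hours earlier (protocol 12.2): 57 / 30.4375 = 1.87 months;
- entry on Day -2, before radiation (assumption): 59 / 30.4375 = 1.94 months.

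**3. How many patients contribute.** Twenty-one patients are treated only if stage I has at least one response among 12, so the expected count is conditional on that:
- ORR 5%: 12 × 0.05 / (1 − 0.95¹²) + 9 × 0.05 = 0.6 / 0.4596 + 0.45 = 1.8.
- ORR 20%: 12 × 0.20 / (1 − 0.80¹²) + 9 × 0.20 = 2.4 / 0.9313 + 1.8 = 4.4.

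That is about 2 to 4 responders. As an illustration, assume three responders, all with events, at 5.55, 7.39 and 11.99 months from first response. The median is 7.39. If the middle patient is the one above and is timed from best response, the values are 3.71, 5.55 and 11.99 and the median is 5.55.

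**4. CBR.** Each evaluable patient without a week-16 scan moves the rate by 1/21 = 4.8 percentage points.

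**The case against.** The SAP is marked as a draft. The multiplication is plainly a slip, and a result in the thousands of months would almost certainly be caught. DOR is descriptive, few patients contribute to it, and the two SAP start dates agree unless a response deepens. All of this stands. It limits the severity and shifts the weight from the unit error to the start date and the missing censoring date. It removes neither fault, since no other section corrects them.

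Three stronger readings are tempting, and the documents do not support them:

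- **That SAP 3.5 is untrue.** DOR does differ from the protocol supplied here. But the SAP was written for the November 7, 2016 version, which is not available, and SAP 3.1.1 still describes durvalumab through Cycle 12 where the current protocol has Cycle 24. Only the need to update the version cited is established.
- **That the SAP and protocol contradict each other on CBR.** In protocol 3.2.1 the 16-week time point may govern PR, CR and SD alike, as the aim sentence suggests. That reading nearly matches SAP 7.2.1. A conflict arises only if PR or CR at any time was meant.
- **That protocol 11.0 already says an unconfirmed PD is not progression.** It lets certain asymptomatic patients continue to the next scan and dates a confirmed progression. The Table 8 footnote asks for confirmation only with new lesions or suspected flare. Neither classifies an unconfirmed PD.

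The missing-scan gap is also partly covered. Protocol Table 2 schedules a scan after Cycle 4, and section 8.2.2 asks patients who stop early to complete the Table 2 assessments. This lowers the number of such patients but does not say how to count them.

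**Conclusion.** The DOR point holds and should be fixed. The conversion in SAP 3.4 is wrong as written, by a constant factor of 926. The three start dates are real, death ends DOR only in the SAP, and neither document sets a censoring date.

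The start date is the more consequential part. It is worth about 1.8 to 1.9 months for any week-8 responder when entry-based timing is compared with first response, and more if entry is earlier than assumed. For a patient whose response deepens as in the example, the two SAP definitions give 7.4 versus 3.7 months. These sizes rest on hypothetical scan dates. The count of about 2 to 4 responders assumes true ORRs of 5% to 20% and a trial that reaches 21 patients.

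For CBR, what holds is the absence of a rule for a missing week-16 scan, at 4.8 points per patient.

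A reader might infer that the trial's conclusion is at risk. It is not: the stage I rule (stop at 0 of 12) and the final rule (3 or more of 21) use ORR alone and are untouched.

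**What to change.** - **SAP 3.4:** replace the formula with DOR (months) = (end date − first response date + 1) × 12 / 365.25.
- **SAP 3.4, SAP 7.2.2 and protocol 3.2.2:** use one definition. Responders only; from first CR or PR to progression or death, whichever is earlier; censored at the last tumour assessment; confirmed progression dated to the initial scan, as in protocol 11.0.
- **Unconfirmed PD:** the sponsor should state how it is classified for DOR and CBR, because protocol 11.0 and Table 8 leave this open.
- **SAP 7.2.1:** state that patients without a documented CR, PR or SD at the week-16 assessment count as no benefit and stay in the denominator, and set a window for that assessment. If response at any time was intended, the SAP and protocol 3.2.1 should both say so.
- **SAP 1 and 3.5:** cite the current protocol version, and list the DOR difference if one remains after alignment.

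The cost is one line of code and some wording in the SAP and in protocol 3.2.1 and 3.2.2. No new data or patients are needed. The downside is that DOR will be shorter than under the entry-based protocol definition, and CBR may fall slightly if any patient lacks a week-16 assessment.

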3.5 Changes to Protocol

No change has been done from the analyses planned in the protocol.

4. Study Patients

4.1 Disposition of Patients

Table describing number of patients screened, entered, treated, and evaluable.

4.2 Protocol Deviations

Protocol deviations will not be analyzed since they are not recorded on the eCRF.

4.3 In- and Exclusion Criteria

This will not be analyzed since specific criteria are not collected on the eCRF.

5. Demographic and Other Baseline Characteristics

Descriptive statistics with respect to patient characteristics at baseline will be displayed for [the ITT population].

The summary of demographic data and baseline disease characteristics will present the following variables:

- Age, sex, race, and ethnicity
- ECOG performance status (0 to 1)
- Time since initial diagnosis of colon cancer

6. Safety Evaluation

The safety analyses will be presented on the [ITT population].

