- Non-sterilized males who are sexually active with a female partner of childbearing potential must use a male condom plus spermicide from screening through 6 months after receipt of the final dose of durvalumab and tremelimumab combination therapy and for an additional 3 months after receipt of the final dose of durvalumab monotherapy.
- Not engaging in sexual activity is an acceptable practice; however, occasional abstinence, the rhythm method, and the withdrawal method are not acceptable methods of contraception.
- Male patients should refrain from sperm donation throughout this period.
- Female partners (of childbearing potential) of male patients must also use a highly effective method of contraception throughout this period ([Table 9](#)).

Highly effective methods of contraception

Highly effective methods of contraception defined as one that results in a low failure rate (i.e., less than 1% per year) when used consistently and correctly are described in [Table 9](#). *Note:* Some contraception methods are **not** considered highly effective (e.g., male or female condom with or without spermicide; female cap, diaphragm, or sponge with or without spermicide; non-copper containing intrauterine device; progestogen-only oral hormonal contraceptive pills where inhibition of ovulation is not the primary mode of action [excluding Cerazette/desogestrel which is considered highly effective]; and triphasic combined oral contraceptive pills).

Table 9. Highly Effective methods of contraception (<1% failure rate)

Barrier/Intrauterine Methods	Hormonal Methods

- Copper T intrauterine device- Levonorgesterel releasing intrauterine system (e.g., Mirena®)^a	
- Etonogestrel implants: e.g., Implanon or Norplant- Intravaginal device: e.g., ethinylestradiol and etonogestrel- Medroxyprogesterone injection: e.g., Depo-Provera- Normal and low dose combined oral contraceptive pill- Norelgestromin/ethinylestradiol transdermal system- Cerazette (desogestrel)

^aThis is also considered a hormonal method.

Statistical Analysis Plan

SPONSOR:	NSABP
PROTOCOL TITLE:	A Phase II Study of the Dual Immune Checkpoint Blockade with Durvalumab (MEDI4736) plus Tremelimumab Following Palliative Hypofractionated Radiation in Patients with Microsatellite Stable (MSS) Metastatic Colorectal Cancer Progressing on Chemotherapy
STUDY CODE:	NSABP Protocol FC-9
Version	Draft July 06, 2019

For Biostatistics:

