Author: [name], Consulting Statistician

For Sponsor:

Reviewer: [name], Project Data Manager

Approver: [name], Clinical Research Physician

Table of Contents

1. INTRODUCTION	3
2. STUDY DESIGN AND OBJECTIVES	3
2.1 Study Objectives.....	3
2.1.1 Co-Primary Objectives	3
2.1.2 Secondary Objectives	3
2.2 Study Design.....	3
2.2.1 Stage I futility analysis	3
2.2.2 Stage II	3
2.3 Sample Size Justification.....	4
3. GENERAL ANALYSIS DEFINITIONS	4
3.1 Study Period and Visit Window Definitions.....	4
3.1.1 Study Periods	4
3.1.2 Entry, Treatment, and Follow-up	4
3.2 Planned Analyses	4
3.2.1 Stage I Analysis	4
3.2.2 Final Analysis.....	5
3.3 Definition of Analysis Populations.....	5
3.3.1 Intent-to-Treat Population (ITT).....	5
3.4 Calculated Variables	5
3.5 Changes to Protocol	5
4. STUDY PATIENTS.....	5
4.1 Disposition of Patients	5
4.2 Protocol Deviations	5
4.3 In- and Exclusion Criteria.....	6
5. DEMOGRAPHIC AND OTHER BASELINE CHARACTERISTICS.....	6
6. SAFETY EVALUATION.....	6
6.1 Extent of Exposure.....	6
6.2 Adverse Events.....	6
6.3 Deaths	7
7. EFFICACY ANALYSIS.....	7
7.1 Primary Analysis of Stage II: Objective Response Rate	7
7.2 Secondary Efficacy Analyses.....	7
7.2.1 Clinical Benefit Rate.....	7
7.2.2 Duration of Response.....	8
8. EXPLORATORY TRANSLATIONAL STUDIES.....	8
9. APPENDICES.....	8
APPENDIX 1: LIST OF STATISTICAL TABLES	9
APPENDIX 3: LIST OF DATA LISTINGS	10

1. Introduction

This Statistical Analysis Plan (SAP) is written for the clinical trial protocol NSABP FC-9, version dated November 7, 2016. The ICH guideline E3 "Structure and Content of Clinical Study Reports" was used as a guide to the writing of the plan.

2. Study Design and Objectives

The FC-9 study is designed as a phase II, open label, single arm study of the dual immune checkpoint blockade with the combination of durvalumab and tremelimumab following hypofractionated palliative radiation in patients with microsatellite stable (MSS) metastatic colorectal cancer (mCRC) who have progressed on chemotherapy.

Study design is a Simon two-stage design (12 patients stage I, 9 patients stage II).

If at least one patient in the first stage have an objective response, the study will proceed to Stage II (*expansion cohort*). The expansion cohort will enroll 9 additional patients. If ≥ 3 patients have objective response, the study therapy will be considered for further testing.

There will be up to 21 evaluable patients (unevaluable patients will be replaced).

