3.3 Definition of Analysis Populations

3.3.1 Intent-to-Treat Population (ITT)

The Intent-To-Treat population (ITT) will consist of patients who complete both Cycle 1 and Cycle 2, and undergo the first restaging scan after Cycle 2 for the determination of tumor response will be determined as evaluable. Non-evaluable patients will be replaced.

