6.1 Extent of Exposure

The exposure to each study drug will be summarized in terms of:

- Number of started cycles
- Total cumulative dose

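### SAP Section 6 puts the safety analyses on the evaluable-only ITT set, Appendix 1 puts the AE and death tables on the Safety set, and the discontinuation and exposure tables stay on ITT

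*Combined protocol and SAP*

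**What the plan says.** The safety population is given in several places in the SAP, which is marked "Draft July 06, 2019".

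- **Section 6, Safety Evaluation:** "The safety analyses will be presented on the [ITT population". The population name is a bracketed field.
- **Section 3.3.1** defines ITT as "patients who complete both Cycle 1 and Cycle 2, and undergo the first restaging scan after Cycle 2". Non-evaluable patients are replaced, so the number dosed can exceed the number in ITT.
- **Section 3.3.2:** "The Safety population will consist of all patients who receive at least one dose of any study medication".
- **Appendix 1** assigns Tables 04.01 ("Summary of Adverse Events") to 04.07 (deaths) to Safety. It assigns Tables 01.02 ("Completion Status and Discontinuation from study drugs"), 01.03 (discontinuation from the study) and 03.01 (exposure) to ITT. Table 01.01 (disposition) is on all enrolled patients.
- **Section 6.1** places exposure within the safety evaluation: "The exposure to each study drug will be summarized in terms of" started cycles and cumulative dose.
- **List of Data Listings:** every listing covers all patients.

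On a related point, SAP 6.2 says that only treatment-emergent AEs are collected. Protocol 10.7.1 records SAEs related to study participation from the time of consent.

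**The concern.** Safety is a secondary objective in both documents. A patient drops out of this ITT set by not completing two cycles or not having the first scan. Among the reasons are early toxicity that leads to stopping under protocol 8.2 and Table 7, and early death. The exclusion is therefore related to the outcome that the safety tables are meant to describe.

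If Section 6 is followed, AEs, toxicity stops and deaths in dosed patients who never became evaluable are absent from the safety summary tables and survive only in listings. If Appendix 1 is followed, the AE and death tables cover everyone dosed, but the discontinuation and exposure tables describe only those who completed two cycles and were rescanned. Table 04.04 (AE-related discontinuation, Safety) could then count patients who do not exist in Table 01.02. Table 01.01 would show how many dosed patients were not evaluable, but not why they stopped.

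**Working it through.** **1. Population by source.**

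| Output | Section 6 text | Appendix 1 |
|---|---|---|
| AE and death tables 04.01–04.07 | ITT | Safety |
| Exposure 03.01 (SAP 6.1) | ITT | ITT |
| Discontinuation 01.02, 01.03 | not covered | ITT |

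The first row is a direct contradiction. The second is consistent now, but would no longer be if Section 6 alone were corrected. The third is a gap whichever text prevails.

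**2. The plan's own figures.** The SAP and protocol give no number for this point. The two-stage design figures in protocol 14.2 reproduce: 0.95^12 = 0.540 for early termination and 12 + 0.460 × 9 = 16.14 for expected size. Exact calculation also gives type I error 0.080 and type II error 0.197. None of them depends on the safety population.

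**3. Early stops missing from Table 01.02.** Let k be the dosed patients who stopped before completing Cycle 2, with 21 evaluable. By the definition of ITT, Table 01.02 shows 0/21 such stops. The true share is k/(21 + k). The values of k are assumptions:

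- k = 0: 0%
- k = 3: 3/24 = 12.5%
- k = 6: 6/27 = 22.2%
- k = 9: 9/30 = 30.0%

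**4. Whether such k are plausible.** If a proportion r of dosed patients is excluded, reaching 21 evaluable requires 21/(1 − r) dosed, with 21r/(1 − r) excluded. Two protocol figures can be used as illustrations.

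- *Toxicity stops.* Protocol 2.5 reports 20/102 = 19.6% stopping this combination for drug-related AEs at any time, in lung cancer and across dose cohorts. If none, half or all of that rate fell before completion of Cycle 2 (r = 0, 0.098, 0.196), the excluded number is 0, 2.3 or 5.1 among 21, 23.3 or 26.1 dosed.
- *Early deaths.* Protocol 2.1 gives a median survival of about 5 months on best supportive care. Two cycles are 56 days, or 1.840 months. Assuming exponential survival, 1 − 2^(−1.840/5) = 22.5% die within that time, giving 6.1 excluded of 27.1 dosed. With an assumed median of 10 months, 1 − 2^(−1.840/10) = 12.0%, giving 2.9 of 23.9.

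Nine excluded is a wider stress case.

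**5. Effect on an AE rate.** Assume 8/21 = 38.1% with a Grade 3/4 AE in ITT. The all-dosed rate lies between the case where no excluded patient had one and the case where all did:

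- 24 dosed: 8/24 = 33.3% to 11/24 = 45.8%
- 27 dosed: 8/27 = 29.6% to 14/27 = 51.9%
- 30 dosed: 8/30 = 26.7% to 17/30 = 56.7%

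The ITT figure lies inside every range, so the direction of bias cannot be fixed in advance.

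**6. Exposure.** Patients who stop before completing Cycle 2 have at most two started cycles, so leaving them out raises mean exposure. Other non-evaluable patients may have more: protocol 8.2.1 lets held therapy resume at the next scheduled cycle and does not settle whether a held cycle is skipped or delayed. The net direction is open.

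**The case against.** The strongest reply is that the practical effect is small. Appendix 1 is the table-level specification and already has all seven AE and death tables right. The conflicting phrase is a bracketed field in a draft. Table 04.04 shows AE-related stops on Safety, and the listings cover every patient in a study small enough to read line by line. The monthly review in protocol 14.3 is not limited to evaluable patients, so monitoring is not impaired. All of this stands, and it keeps the point well below a threat to the trial. It does not remove the contradiction, and listings do not supply summary rates.

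On the remedy, Safety is not the only defensible set for Table 01.03; all enrolled patients would also do. Only the titles of Tables 01.02 and 01.03 are given, so it is not certain that they would report reasons for stopping. Baseline Table 02.01 would still be on ITT. The root cause is that an evaluable-only set is called ITT. Each of these is fair. Redefining ITT, however, would also change the denominator of the efficacy tables, which is a larger decision than this point needs.

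On size, the lung cancer and best-supportive-care figures come from other populations, and this trial's eligibility (ECOG 0–1, adequate organ function) may make early death less common than the exponential illustration suggests. That is why they are offered only as illustrations.

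On SAP 6.2, protocol 10.8 does start routine AE recording at the first dose, so the sentence is wrong only for participation-related SAEs before dosing. That part is minor.

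**Conclusion.** The concern holds and should be fixed before the SAP is finalised. Section 6 and Appendix 1 name different populations for the AE and death analyses. Separately, Tables 01.02, 01.03 and 03.01 leave out dosed patients who never became evaluable, whichever text prevails on the AE tables.

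The contradiction and the exclusion follow from the text and need no assumption. Their numerical size does: it is zero if every dosed patient becomes evaluable, and 12.5% to 30.0% of dosed patients for 3 to 9 early stops alongside 21 evaluable. The direction of bias in AE rates and in mean exposure cannot be determined. The response-rate decision rule is not affected.

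The SAP's table of contents has an entry for 3.3.1 but none for 3.3.2. This suggests that the Safety set was added later and Section 6 was not updated. That is an inference only; the same table of contents is out of step with the text elsewhere (it lists co-primary objectives where the text has one primary objective).

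**What to change.** 1. In SAP Section 6, replace the bracketed ITT population with the Safety population of SAP 3.3.2.
2. In Appendix 1, change the population of Tables 01.02, 01.03 and 03.01 from ITT to Safety, so that discontinuation, exposure, AE and death tables share one denominator. All enrolled patients would also be acceptable for Table 01.03 if the sponsor prefers it.
3. In SAP 6.2, amend the sentence on treatment-emergent AEs to acknowledge the participation-related SAEs recorded from consent under protocol 10.7.1.

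The cost is one phrase, three table labels and one sentence. No new data and no protocol amendment are needed.
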